In all circumstances where data are shared, only de-identified data will be made available. If identifiable data are requested, the requesting researcher will need to complete a full IRB process prior to approval.

Confidentiality will be maintained at all study sites whenever possible. All specimens and data will be de-identified and coded. Reports will be submitted to the clinical management team for Determining Cause of Death (DeCoDe) meetings. De-identified data will be shared with surveillance teams of the MoH and respective hospitals for further analysis and for data to action. Summary de-identified feedback to individual physicians will be provided for the purpose of improvement of quality of clinical care. Coded confidential reports that lack identifying information will be issued to next of kin during debrief sessions. Loss of confidentiality may occur when notifiable diseases such as TB, HIV or SARS-COV-2 infection is confirmed and shared with MoH disease surveillance teams, who may perform contact tracing to require testing and isolation/treatment of contacts of the deceased. The principal investigators will liaise with relevant hospital and national surveillance teams to manage this process by adhering to national laws and relevant policies.

De-identified verbal autopsy data and COVID results will be shared with the World Health Organization's Verbal Autopsy Technical Advisory Group (TAG) for their internal analysis and use.

Publicly available data will be reported to relevant stakeholders regularly and may include aggregate data and analyses regarding causes of death in the community and de-identified case data for training and secondary analyses.

Results from the study may additionally be presented at scientific conferences and/or in peer-reviewed manuscripts to contribute to the body of knowledge of childhood morbidity and mortality. A publications committee will be constituted by the PO and sites to review proposed publications involving more than one site's data. Sites will have similar mechanisms for reviewing proposed uses of site-specific data.

Version: 1.0, 8/22/2022

21. Plans to Monitor the Data to Ensure Safety of Participants and Data Integrity

No more than minimal risk

22. Provisions to Protect the Privacy Interest of Participants

The next of kin of the deceased persons will be contacted by study staff. Supportive and grief counselling by trained staff will be offered before, during and after the consent process.

23. Economic Burden to Participants

There is no economic burden to participants, except costs of phone calls for and transportation for consent and verbal autopsy. Any such costs will be covered by CHAMPS.

24. Informed Consent

The next of kin of the deceased persons will be contacted by site study staff. Supportive and grief counselling by trained site staff will be offered before, during and after the consent process. Next of kin who are listed within the medical records will be contacted to consent on behalf of the dead persons. During this period, the study will be explained and informed consent for MITS will be sought. Spouses of deceased persons or close relations with power of attorney are eligible to offer informed consent.

Informed consent procedures are specified in site-specific protocols (Appendices A and B); informed consent forms (Appendices F and G) have been approved by appropriate IRBs (Appendices D and E).

Emory staff will never receive ICFs and will not have access to names.

25. Setting

Site settings are described in local IRB protocols (Appendices A and B).

26. Resources Available

Resources are described in local IRB protocols (Appendices A and B).

27. Multi-Site Research When Emory is the Lead Site

The CHAMPS Network currently consists of 7 sites in Sub-Saharan Africa and South Asia. Plans for adding additional sites are in progress. Each site participating in this study will obtain local IRB approval prior to beginning the study. The target sample size is 200-300 MITS cases per site. Data will be stored locally as described in Data Management and Confidentiality.

The CHAMPS PO at Emory University will not be involved with the consent process and will not directly interact with study participants. The CHAMPS PO will receive data from site and support sites in the following activities:

- 1. Technical assistance in adaptation and implementation
- 2. Data management, including data quality assurance and quality control
- 3. Specimen reference testing and archive

Page 20 of 33 Version: 1.0, 8/22/2022

4. Data analysis and dissemination of findings to key stakeholders

Sites will be closely linked to the PO through an established formal reporting structure.

28. References

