Study Population	All adult deaths (18 years and above) among residents of Child Health and Mortality Prevention Surveillance (CHAMPS) catchment areas.
Sample Size	200-300 adult deaths per site
Study Duration for individual participants	Prospective enrollment for a period of at least 14 months to include at least 2 peak malaria seasons or until target sample size is achieved
Study Specific	Abbreviations
Abbreviations/ Definitions	BMGF: Bill and Melinda Gates Foundation
	CDA: Complete Diagnostic Autopsies
	CDC: Centers for Disease Control and Prevention
	CHAMPS: Child Health and Mortality Prevention Surveillance
	COMSA: Countrywide Mortality Surveillance for Action
	CPL: CHAMPS Pathology Laboratory
	DeCoDe: Determination of Cause of Death
	HDSS: Demographic Surveillance System
	MITS: Minimally Invasive Tissue Sampling
	MoH: Ministry of Health
	PCR: Polymerase Chain Reaction
	PO: Program Office
	PPE: Personal Protective Equipment

SBS: Social Behavioral Science

TAC: TaqMan Array Cards

WHO: World Health Organization

Definitions

Adult: Individual aged 18 years or above.

Catchment area: Area from which hospital draws patients or defined demographic surveillance area, as appropriate for site.

CHAMPS Program Office: A unit comprised of staff from the Emory Global Health Institute, the Centers for Disease Control and Prevention, The Task Force for Global Health (Public Health Informatics Institute), the International Association of National Public Health Institutes, and other stakeholders, which develops protocols and procedures for CHAMPS and provides technical assistance to sites for implementation, under the direction of the prime awardee, Emory University.

Death: Irreversible cessation of all cardiorespiratory function, as certified by the attending clinician or study staff.

Traumatic death: Death due to injuries, traumarelated death, and death due to a natural disaster or conflict.

Notified adult death: All deaths occurring among adults (18 years or above) that are reported through CHAMPS mortality surveillance in health facilities or communities or demographic surveillance.

Funding Source (if any)

Bill and Melinda Gates Foundation

2. Objectives

General aim: To assess the role of malaria and other infectious disease etiologies in areas endemic for various infectious diseases by applying minimally invasive tissue sampling (MITS).

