The vision for the CHAMPS Network specimen archive is to create a standardized, reliable, quality management approach to the collection, storage, access, and use of CHAMPS Network specimens with equitable governance by the global public health community. Supporting high-quality specimen collection, maintaining long-term specimen integrity, preserving patient confidentiality and privacy, and establishing robust governance procedures are core objectives. Frozen tissues and non-tissue specimens would be stored at -80°C at surveillance sites and under liquid nitrogen (-140°C) at a central facility (initially at the CHAMPS CPL long-term storage facility). All tissue specimens processed will be stored as formalin-fixed paraffin blocks (FFPE) and slides. The location and key findings will be recorded in the CHAMPS database.

9. Sharing of Results with Participants

The CHAMPS site investigators will provide two opportunities for feedback to the family of the deceased: preliminary feedback within one month from the date of death, and final feedback following the DeCoDe determination of cause of death. CHAMPS will work with the local health authorities to determine which laboratory, clinical or other MITS findings may have ethical or public health implications (e.g., reportable diseases, preventable infections, intentional injuries), and apply similar policies as CHAMPS to undertake basic actions to improve the family's health status.

10. Study Timelines

Once families consent to the MITS procedure after all their questions have been answered, the procedure itself takes approximately 60 minutes to complete. Enrollment for MITS at two CHAMPS sites has already begun in August 2022 via protocols approved by local IRBs (Appendices D and E), with the goal of enrolling deaths during the peak malaria months in 2022 and continuing through the peak malaria months in 2023 (for a total of 14 months of enrollment). Additional CHAMPS sites with approved local protocols will aim for similar durations.

11. Inclusion and Exclusion Criteria

Inclusion criteria

- 1. Deceased adults, aged 18 years and above, and
- 2. Resident member of at least one of the CHAMPS catchment areas, and
- 3. Where the next of kin provides informed consent, and
- 4. Death occurred <24 hours before enrollment

Exclusion criteria

- 1. Mortality in individuals aged <18 years
- 2. Trauma-related deaths, including falls, drowning and road-traffic and other accidental accidents

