Page 16 of 33 Version: 1.0, 8/22/2022

3. Non-resident of the local CHAMPS catchment areas

12. Population

As death notifications are received by CHAMPS site study staff, all eligible adult deaths in the CHAMPS catchment areas will be recruited using consecutive convenience sampling.

This human subject research does not meet the definition of 'Clinical Research.' However, there are still important ethical considerations, including concerns of family members, to take into account, which are ethical and not regulatory human subjects concerns.

Deceased persons have been previously determined by institutional review boards not to be human subjects. In this study, those enrolled will all be 18 years of age and above.

13. Vulnerable Populations

This human subject research does not meet the definition of 'Clinical Research.' However, there are still important ethical considerations, including concerns of family members, to take into account, which are ethical and not regulatory human subjects concerns.

Deceased persons have been previously determined by institutional review boards not to be human subjects. In this study, those enrolled will all be 18 years of age and above.

14. Local Number of Participants

Each CHAMPS site will target 200-300 MITS cases. All eligible adult deaths in the CHAMPS catchment areas will be recruited using consecutive convenience sampling. MITS activities will be discontinued after the target number of deceased MITS cases is reached and enrollment covers at least two malaria seasons.

15. Recruitment Methods

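### The Study Summary and Section 14 give different rules for ending enrolment, so a fast site could stop before a second malaria season and its malaria share would depend on the stopping date

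*Protocol*

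**What the plan says.** The duration row of the Study Summary (Section 1) sets prospective enrolment for "at least 14 months to include at least 2 peak malaria seasons or until target sample size is achieved".

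Section 14 (Local Number of Participants) says: "MITS activities will be discontinued after the target number of deceased MITS cases is reached and enrollment covers at least two malaria seasons". The same section gives the target: "Each CHAMPS site will target 200-300 MITS cases". Under Sections 12 and 14, eligible deaths "will be recruited using consecutive convenience sampling".

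Section 10 (Study Timelines) gives the calendar. "Enrollment for MITS at two CHAMPS sites has already begun in August 2022", "with the goal of enrolling deaths during the peak malaria months in 2022 and continuing through the peak malaria months in 2023", 14 months in all. For later sites: "Additional CHAMPS sites with approved local protocols will aim for similar durations".

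Section 7 plans, for the primary objective, a descriptive distribution of deaths by malaria, other infectious and non-communicable causes at each site. It introduces this as a list of approaches that may be used. It mentions neither season nor calendar month.

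**The concern.** The two rules differ in what they allow. With 'or', a site that reaches 200 deaths quickly may stop with one season covered, or part of one, and a slow site may stop at 14 months short of its target. With 'and', neither may stop. Sites work under their own local protocols, so different sites could follow different rules. A later analysis plan cannot repair this, because it cannot supply months that were never sampled.

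The rule bears on the primary objective, malaria's contribution to adult death. By asking for two peak seasons, the protocol itself treats season as relevant. Recruitment is consecutive, so the months a site is open decide its mix of peak and off-peak deaths. If sites stop at different points of the year, their malaria shares are not comparable. A larger sample does not remove the difference.

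**Working it through.** **The plan's own figures.** Section 7 uses n = N z² p(1−p) / ((N−1)d² + z² p(1−p)), with N = 32,000, z = 1.96 and d = 0.05.
- p = 0.15: 15,673.7 / 80.487 = 194.7, so 195.
- p = 0.10: 11,063.8 / 80.343 = 137.7, so 138.

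Both reproduce. The sample size is not at issue.

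**The two rules side by side.**

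| Site | Study Summary ('or') | Section 14 ('and') |
|---|---|---|
| Target reached in month 6, one season | may stop | must continue |
| 14 months, two seasons, target not reached | may stop | must continue |
| Target reached and two seasons covered | may stop | stops |

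**Inputs for the size of the bias.** From the protocol: a malaria share of 10–14% (Sections 4 and 7; 12% taken here), 200–300 deaths per site, and a 14-month window from August 2022. Assumed, because the protocol gives no values: k peak months a year (2 or 4), a peak share R times the off-peak share (2 or 3), and equal enrolment each month. The reference is the share over one full 12-month cycle, p.

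- Off-peak share = 12p / (kR + 12 − k); peak share = R × off-peak share.
- Six-month stop starting at a peak = (k × peak + (6 − k) × off-peak) / 6.
- 14 months with two peak months repeated = ((k + 2) × peak + (12 − k) × off-peak) / 14.

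| k | R | Peak | Off-peak | 6-month share | Bias (points) | 14-month share | Bias (points) |
|---|---|---|---|---|---|---|---|
| 2 | 2 | 20.6% | 10.3% | 13.7% | +1.7 | 13.2% | +1.2 |
| 2 | 3 | 27.0% | 9.0% | 15.0% | +3.0 | 14.1% | +2.1 |
| 4 | 2 | 18.0% | 9.0% | 15.0% | +3.0 | 12.9% | +0.9 |
| 4 | 3 | 21.6% | 7.2% | 16.8% | +4.8 | 13.4% | +1.4 |

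Example for k = 4, R = 3: off-peak = 1.44/20 = 7.2%; peak = 21.6%; six months = (4 × 21.6 + 2 × 7.2)/6 = 16.8%.

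A site open only for the other six months would err by the same amount downward: 2 × 12 − 16.8 = 7.2%. The sign therefore depends on the start month, which the protocol gives only for the first two sites.

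Reaching 200 in six months means 200/6 = 33 a month, against 200/14 = 14 (300/14 = 21) for a site that fills the planned window.

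**Comparison with precision.** The 95% half-width at n = 200 and p = 12% is 1.96 × √(0.12 × 0.88/200) = 4.5 points.

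**Which months repeat at 14 months.** August 2022 plus 14 months runs to about September 2023, so about August and September occur twice. If there is one peak a year, this window can reach both the 2022 and the 2023 peak only if the peak overlaps those two months. With two peaks a year that need not follow. For k = 4, peak months become 6/14 = 42.9% of enrolment instead of 4/12 = 33.3%.

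**Cost of standardising.** Ten months have weight 1 and four (two calendar months, each seen twice) have weight 0.5. The design effect is 14 × (10 + 4 × 0.25) / (10 + 4 × 0.5)² = 14 × 11/144 = 1.069. The interval widens by √1.069 = 1.034, about 3%.

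**The case against.** The strongest reply is that this is one loose line in a summary table. It could be meant as whichever condition comes later, and Section 14 is explicit. Section 10 plans about 14 months, so an early stop may never happen. Section 7 also has each site review its data after 25–50 deaths and again after 100, to keep the sample as representative as possible. A site nearing its target early would be noticed.

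Part of this stands. The intention is probably the stricter rule, and the review would make fast enrolment visible. But the Summary does not say which condition governs, season is not among the features listed for the review, and that review concerns who is sampled, not when a site closes.

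On the 14-month window, it is fair to say that covering two peaks is a defensible choice, that the lean is well inside the half-width, and that a minimum of 14 months permits a longer period. Weighting is also detail that a separate analysis plan may hold.

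A reader might infer more than the protocol supports:
- **A sample drawn wholly inside one peak.** With an assumed four-month peak and shares of 20% and 8%, the bias would be 20 − 12 = 8 points, and more under stronger seasonality. That needs at least 200/4 = 50 completed procedures a month. The 32,000 deaths a year in Section 7 are not identified as one site's pool, and consent, residency, the time limit and the trauma exclusion all reduce it.
- **August as a stated peak month.** Section 10 names no peak month; the overlap is an inference.
- **An annual estimand and an unweighted analysis.** The objectives do not say annual, and Section 7 does not say unweighted. It states no seasonal correction.
- **The whole peak counted twice.** Only about two calendar months repeat.

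**Conclusion.** The conflict between the Study Summary and Section 14 is certain and must be reconciled, because it decides whether a site may close before a second malaria season. If a site closed after six months starting at a peak, its malaria share would be too high by about 1.7 to 4.8 points. At the upper end that matches the whole half-width at n = 200. This assumes a 12% share, 2 to 4 peak months, a peak share 2 to 3 times the off-peak share and even enrolment. No seasonal figure comes from the protocol, so the range is illustrative.

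The lean from the planned 14 months is a secondary matter: about +1 to +2 points on the same assumptions, with one peak a year. It is systematic but modest, and does not by itself undermine the design.

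**What to change.** **Required.** In the duration row of the Study Summary, replace the 'or' alternative with the Section 14 rule: enrolment ends when the target is reached and at least two malaria seasons are covered. Align the site protocols with it. Recruitment should stay consecutive. Slowing a fast site to about 14–21 deaths a month would mean passing over eligible deaths, contrary to Sections 12 and 14. The costs are that a fast site may exceed its target and that a slow site loses the 14-month exit.

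**Recommended.** In Section 7, report the malaria proportion standardised to one 12-month cycle beside the crude proportion. Weight each calendar month by its share of tracked eligible deaths, with a month seen twice sharing one month's weight. Section 6 already has all notified deaths tracked and their eligibility determined, so the weights need no new data collection. The interval widens by about 3%, from 4.5 to about 4.7 points at n = 200 (4.5 × 1.034).

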- 6. Occupational Health Care: All study personnel will be required to undergo medical follow-up. These will include vaccination for hepatitis B, Influenza, tetanus and pertussis. Regular COVID-19 testing will be performed as defined by national guidelines and those who test positive will undergo isolation as defined by national guidelines. Personnel will receive regular grief counselling and debrief. They will be encouraged to maintain social distancing and adhere to COVID-19 prevention regulations

7. Statistical Analysis Plan

Sample size determination

Our sample size determination method was adopted from a method which has been detailed elsewhere.²⁴ In brief, below is our sample size estimates:

 $n=(Nz^2p(1-p)/((N-1) d^2+z^2p(1-p))$

n = minimum sample size

N = Number of adult mortalities, per year (32,000)

Z = z value 1.96 at 5% type 1 error, 95% confidence level

p = prevalence of adult respiratory disease mortality (estimated at 15% of all adult mortalities)

d = margin of error taken as 0.05

The minimum sample size needed for respiratory disease mortality is 195. The estimated prevalence of adult malaria mortality is 10-14% per site, which will require a smaller target sample size (n=138 at 10% prevalence). This study plans to enroll 200 or more adults at each site.

Interim analysis

A preliminary evaluation of data will be conducted by each site after 25-50 deaths with completed MITS. Case demographics and malaria test results will be assessed to determine whether criteria for enrollment needs to be adjusted (e.g. representation of likely malaria deaths, rural-urban residence, gender balance, community versus hospital deaths). The CHAMPS site study team (in collaboration with the CHAMPS PO) will analyze the initial data on deaths at each site in order to recommend measures aimed at making deaths selected for MITS as representative as possible within resource constraints, and/or to recommend differential sampling of certain age groups and/or types of deaths in order to optimize the resources allocated for MITS. A similar interim analysis will be conducted after 100 deaths.

Purpose: To identify issues that will affect our approach to the primary analysis. Specifically:

- To assess the distribution of age groups and malaria positivity by different testing methods
- 2. To summarize the amount of missing data for key variables

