- 3. To examine the distributional characteristics of key variables in order to detect potential data entry/reduction errors

Methods: Relevant approaches may include:

- 1. Tabulation of descriptive statistics for key variables including missing observations
- 2. Histograms and other data visualizations

Analysis plan for primary objective

Purpose: To assess the relative contribution of malaria and other infectious disease etiologies to death in adults 18 years and above, in each CHAMPS site

Methods: Relevant approaches may include:

- 1. Descriptive analysis to examine the distribution of deceased cases with malaria, infectious and non-communicable disease etiologies
- 2. Descriptive analysis to examine key demographic and clinical characteristics

8. Data and/or Specimen Banking

CHAMPS datasets captured at each CHAMPS site will be maintained at each site in a local secure data repository as well as mirrored in a secure global data repository maintained by the CHAMPS Project Officer based at Emory University. Any physical data collection instruments containing unique identifiers will be stored in closed, locked filing systems with restricted access at CHAMPS study offices at sites, where each site will be the custodian of their respective site study data. The CHAMPS Network global data repository will be a centralized, web-accessible, composite database of CHAMPS Network data from all participating sites that will provide data visualizations and analyses.

Page 15 of 33 Version: 1.0, 8/22/2022

Where indicated, defined specimens will be shipped to the CHAMPS CPL in Atlanta, Georgia, USA, for confirmatory testing and bio banking. This will be the site for quality assurance and shipment of specimens will be guided by approved material transfer agreements and batch shipment requests, with strict adherence to MoHs and local CHAMPS site regulations on shipment of clinical and research biological specimens.

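### Section 7 lets malaria test results prompt a change in enrolment criteria, with no decision rule and against the consecutive-recruitment rule; a malaria-related change pooled unweighted would bias the primary proportion

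*Protocol*

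**What the plan says.** The primary quantity is the contribution of malaria to adult deaths, described per site (protocol Sections 1, 2 and 7). Section 3 gives the purpose as confirming or refuting that malaria contributes significantly to adult mortality. Section 4 promises robust estimates for each location.

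On recruitment, Section 12 states that "all eligible adult deaths in the CHAMPS catchment areas will be recruited using consecutive convenience sampling". Section 14 repeats this and Section 1 describes the same consecutive method. Section 3 adds that enrolment is not restricted to deaths with fever.

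On the interim looks, Section 7 has each site evaluate its data after 25-50 completed MITS and again after 100 deaths. Case demographics and "malaria test results will be assessed to determine whether criteria for enrollment needs to be adjusted (e.g. representation of likely malaria deaths"; the list of examples continues with residence, gender, and community versus hospital death. The site team, in collaboration with the Program Office, is to recommend measures that make the sample as representative as resources allow, and/or "to recommend differential sampling of certain age groups and/or types of deaths in order to optimize the resources allocated for MITS". No threshold, direction or limit is stated.

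For the primary analysis, Section 7 lists as a possible approach "Descriptive analysis to examine the distribution of deceased cases with malaria, infectious and non-communicable disease etiologies". Section 6 (Mortality Surveillance) says that all notified deaths are tracked.

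**The concern.** A proportion estimates malaria's share of deaths only if the chance of being sampled does not depend on malaria, or if that dependence is known and corrected. Section 7 allows interim results on the primary question to influence who is enrolled next, and names the number of likely malaria deaths as a reason. A site that found few malaria positives could sample more deaths of a malaria-like type, and a site that found many could do the reverse. Its final proportion would then partly reflect that decision.

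The provision also conflicts with the recruitment rule. Differential sampling of types of deaths cannot operate while every eligible death is recruited consecutively, and Sections 12 and 14 provide no exception.

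What is at stake is whether the site's malaria proportion can answer the question the study was set up to answer.

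**Working it through.** **1. The plan's own figures.** Section 7 gives n = N z² p(1−p) / [(N−1)d² + z² p(1−p)], with N = 32,000, z = 1.96 and d = 0.05.
- p = 0.15: 32,000 × 0.489804 / (79.9975 + 0.489804) = 194.7, so 195.
- p = 0.10: 32,000 × 0.345744 / (79.9975 + 0.345744) = 137.7, so 138.

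Both stated sizes reproduce, so no arithmetic error is at issue. The formula assumes a sample not selected on the outcome. For malaria, Section 7 says that "The estimated prevalence of adult malaria mortality is 10-14% per site", so true shares of 10% and 12% are used below.

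**2. Assumptions that are not in the documents.** The criteria change at death 50 of 200. After the change one group is selected k times as readily as before relative to the rest, with k = 2 or 0.5. All 200 deaths are pooled without weights: estimate = (50 × p + 150 × p*) / 200, where p* is the malaria share after the change.

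**3. Selection through a proxy.** Enrolment takes place within 24 hours of death (Section 11), before MITS testing is complete and before the panel assigns a cause (target 150 days, Section 6). Selection can therefore act only on features known at enrolment. Assume that 40% of deaths are febrile, with malaria in 22% of these and in 2% of the rest, so p = 0.4 × 0.22 + 0.6 × 0.02 = 10%.
- k = 2: febrile share 0.8 / 1.4 = 0.571; p* = 0.571 × 0.22 + 0.429 × 0.02 = 13.4%; pooled 12.6% (+2.6 points).
- k = 0.5: febrile share 0.2 / 0.8 = 0.25; p* = 0.25 × 0.22 + 0.75 × 0.02 = 7.0%; pooled (5 + 10.5) / 200 = 7.75%, about 7.8% (about −2.3 points).
- Weighting each stratum back to its true share returns 0.4 × 0.22 + 0.6 × 0.02 = 10%.

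**4. Upper bound for the same k: perfect selection on malaria.** p* = kp / (kp + 1 − p).

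| True p | k | p* | Pooled estimate | Shift (points) |
|---|---|---|---|---|
| 10% | 2 | 18.2% | 16.1% | +6.1 |
| 10% | 0.5 | 5.3% | 6.4% | −3.6 |
| 12% | 2 | 21.4% | 19.1% | +7.1 |

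For the last row: 0.24 / (0.24 + 0.88) = 0.2143, and (6 + 32.14) / 200 = 19.1%. If the change comes at death 100 instead, that row becomes (12 + 21.43) / 200 = 16.7%.

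**5. Noise in the looks.** Three malaria deaths in 25 (12%) has an exact 95% interval of 2.5% to 31.2%. At p = 10% the approximate half-width, 1.96 × √(0.09/m), is 11.8 points for m = 25, 8.3 for m = 50 and 5.9 for m = 100. A site could change its criteria in response to chance alone.

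**The case against.** The strongest case on the other side has five parts.

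- **Aim.** Representativeness is a stated aim, and the malaria example sits beside residence, gender and place of death. It can be read as a check on balance, not as enrichment. This is fair, but the text joins that aim by and/or to differential sampling for resource reasons, so the aim does not limit what may be recommended.
- **Who decides.** A reader might infer that each site decides alone. The text does not support that: the output is a recommendation made in collaboration with the Program Office. That oversight still does not supply a rule.
- **Whether bias follows.** A reader might infer that the malaria proportion is already biased. The protocol commits to no change, to none related to malaria, and to no unweighted pooling. The listed analysis approaches are not exhaustive, and a separate statistical analysis plan could specify weights. This stands, so the point does not rest on missing weights. Weighting works only where sampling fractions are known and above zero; if changed criteria exclude a type of death altogether, later weighting cannot recover it.
- **Recruitment rule.** Sections 12 and 14 may be meant as the starting rule, which Section 7 can amend. They do not say so, and the passages need to be reconciled.
- **Comparison of sites.** A reader might infer that the study's between-site comparison is broken. The objectives contain no such comparison; the estimates are per site.

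**Conclusion.** The concern holds in conditional form. Section 7 makes malaria test results a ground for changing enrolment, gives no decision rule, and conflicts with consecutive recruitment of all eligible deaths. A malaria-related change pooled without weights would bias the site's primary proportion in either direction.

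The size cannot be derived from the documents. With the assumed proxy figures, doubling or halving febrile selection from death 50 of 200 moves a true 10% to about 12.6% or 7.8%, which is within the planned 5-point margin. The 19.1% figure (true share 12%, doubling) needs perfect selection on malaria. It is an upper bound for that selection ratio and should not be read as the expected effect, because cause of death is not known at enrolment. All selection ratios and febrile-stratum figures are assumptions.

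**What to change.** In Section 7:

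1. Remove malaria test results and the representation of likely malaria deaths as grounds for changing enrolment. Keep malaria positivity in the looks only for assay and data-quality checks.
2. Permit sampling changes only by declared non-outcome strata (age group, sex, residence, place of death), and set no stratum's sampling fraction to zero.
3. Log the date of any change and each stratum's sampling fraction, taken as MITS divided by eligible notified deaths. The tracking in Section 6 already supplies the denominator.
4. If fractions change, report the malaria proportion weighted by the inverse sampling fraction, with the periods before and after the change as separate strata.
5. Reconcile Sections 12 and 14 with Section 7, so that the recruitment rule and any permitted departure from it are stated consistently.

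There is no need to keep malaria results from those who decide on sampling. Sites run the tests themselves (Section 6), so this would be impractical.

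The cost is protocol wording and, if fractions change, a weighted proportion in place of a raw one. Intervals would be slightly wider where fractions differ, and sites lose the option to enrich for malaria.
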